**Protocol Version 1.13 April 4, 2020**

**1. Background and specific aims:** In the United States (U.S.), Black women are three times more likely to experience iron deficiency (ID) in pregnancy compared to women from other racial/ethnic groups, for reasons that remain largely unknown. Women who are iron deficient during pregnancy experience higher rates of maternal and infant mortality, preterm birth, low infant birth weight, and irreversible neurocognitive defects in their children. Indeed, the highest rates of adverse maternal-infant health outcomes occur in Black women, a phenomenon that may be driven by their sub-optimal iron status. Specific to Chicago, in some low income predominately Black neighborhoods (e.g. Englewood, Austin), preterm birth rates range between 18.5% and 34.8% far exceeding the national average of 9.6% and the state of Illinois at 10.3%. *Exposure to structural violence may compromise maternal iron status that contributes to adverse maternal-infant health outcomes in Black women in at-risk communities.*

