We will monitor adherence using electronic pill monitoring technology Pillsy and standard pill counts. Women will get a new 30-40-day allotment of pills. During these visits, we will download data from the Pillsy app on their smart phones and conduct a physical pill count. If a woman is found to be non-compliant (i.e., consuming <75% of pills) with her permission, she will receive automated daily text messages around dinner time to help increase compliance with the supplement interventions.

**Pill pick up and adherence monitoring visits (approximately @ 18-19 weeks, 22-23 weeks, 30-31 weeks, 38-39 weeks).** We will monitor adherence using electronic pill monitoring technology Pillsy and standard pill counts. Women will visit UIC approximately every 28 days to get a new 30-40-day allotment of pills and for compliance to be assessed. If possible, these encounters will be coordinated around standard clinical prenatal care appointments. If not, separate pill pick up visits and under certain conditions home pill drop-off will be coordinated. During these visits, we will download data from the Pillsy app on their smart phones and conduct a physical pill count. If a woman is found to be non-compliant (i.e., consuming < 75% of pills) with her permission, she will receive automated daily text messages around dinner time to help increase compliance with the supplement interventions. We will administer the GI symptoms checklist at each visit.

- c. Feasibility and Tolerability. Feasibility will be based on accrual and withdrawal/loss to follow-up rates at the end of the study and adherence determined using the Pillsy smart bottles and standard pill counts. The intervention will be considered feasible if 50% of women approached for participation enroll, overall withdrawal rate is  $\leq 15\%$  and adherence to the supplement regimen is  $\geq 85\%$ . Tolerability [(potential adverse events (AEs) (e.g., GI symptoms)] will be assessed via phone/email/text using the Pillsy app weekly for the first 4 weeks and bi-weekly thereafter. The intervention will be deemed tolerable if no serious AEs (highly unlikely) are documented, and the rate of non-serious AEs is similar between study arms.

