**e. Labor and delivery.**

Reminders for contacting research staff and participant tracking. During the 34–36 gestational week research visit and/or at the final pill pick, women will be provided a laminated card with the study number and staff personal contact information. Women will be instructed to contact the research team when they are admitted to UIC labor and delivery. In addition, we will follow the progress of these women closely via phone call, text message, email and through the patient EHR until they are admitted to UIC labor and delivery. UIC labor and delivery staff will also be in-serviced regarding the study procedures.

- 1) Maternal venous blood draw: Following admission, as part of routine care, women will undergo a venous blood collection by labor and delivery staff. As part of this routine care, we will request an additional two tubes of blood (30 ml) for research purposes. If there is extra blood available from the venous blood sample and the patient consents, it may be used for future research to learn more about how to prevent, detect, or treat other health problems in pregnancy.
- 2) Umbilical venous cord blood collection (placental cord blood): Immediately following delivery, the research team will collect a maximum of three tubes of umbilical venous cord blood (~30 mL). If a research participant chooses to bank their umbilical cord blood, and therefore the research team cannot obtain 30 mL of umbilical cord blood, the research team will draw 30 mL of placental blood for analysis. If there is extra cord blood available from the cord blood sample and the patient consents, it may be used for future research to learn more about how to prevent, detect, or treat other health problems in pregnancy.
- 3) Placenta (20 grams): After the cord blood has been obtained, the placenta will be placed in a basin with lid and transferred to the [name] lab space in COMRB. Following placental

characteristics will be examined (i.e., weight, length) and processed for analysis and stored at -80C until later analysis.

- 4) Maternal and infant labor and delivery data: Following participant discharge, a research team member will abstract pertinent maternal and infant L&D data (i.e., route of delivery, infant weight, and infant length) from the EHR.

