#### **XIV. Data and safety monitoring plan.**

The PI will establish a data safety monitoring plan and follow all procedures for the protection of human subjects as required by UIC. The purpose of this data and safety monitoring plan is: (1) to ensure the safety of study subjects and the validity of data; and (2) to produce high quality research while considering both risks and benefits. The PI and research assistants will meet weekly to monitor the components of the research study.

Assessment of study risk. The probiotic proposed for use in the study is not contraindicated during pregnancy and therefore has not been shown to pose any adverse risk to the pregnant woman or her fetus. All other study procedures, based on UIC guidelines should be determined as minimal risk.

Data monitoring plan. The PI will monitor the following items: data quality, completeness, and timeliness; adequacy of compliance with goals for recruitment and retention, including those related to participation of minorities; adherence to the protocol; and adverse events reported by subjects at study and adherence visits. If an adverse event is reported during the study, subjects will be requested to report the event to their physician and the PI. All adverse events will be documented and reported to the UIC IRB in a timely manner based on the type of adverse event (adverse event vs. serious adverse event). We will also record and track reasons for dropout. All authorized study personnel will be required to notify the PI of any unanticipated problems/adverse events immediately upon discovery. The PIs will immediately notify the UIC IRB. The study will be subject to annual review and recertification by the OPRS.

Experimental Aim 2: The Maternal Stress Reduction Project, "Happy Moms" Focus Groups  
Information collected from the focus groups will help inform the development of a curriculum focusing on lifestyle and dietary approaches to reduce chronic stress from structural violence. The curriculum will be developed into a series of classes that will be offered at the New Moms Austin Chicago location. The classes will be open to focus group participants and women currently participating in Family Support programs offered by New Moms.

The Maternal Stress Reduction Project, "Happy Moms": Recruitment, Eligibility, Informed Consent and Data Collection

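### No planned item systematically collects serious events of the birth admission or the newborn, and record data are not linked to the zero-serious-event tolerability rule, so a zero count could not be read as absence of events.

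*Combined protocol and SAP*

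**What the plan says.** - **Source of events.** Section XIV has the PI monitor "adverse events reported by subjects at study and adherence visits". It also obliges all study personnel to tell the PI of any adverse event or unanticipated problem as soon as they discover it.
- **Tolerability rule.** Section VI.c: "The intervention will be deemed tolerable if no serious AEs (highly unlikely) are documented", and in addition the non-serious event rate must be similar in the two arms.
- **Timing.** Section V has both groups take supplements daily up to delivery. The separate pill pick-up visits are "approximately @ 18-19 weeks, 22-23 weeks, 30-31 weeks, 38-39 weeks". At these visits, "We will administer the GI symptoms checklist at each visit". Tolerability between visits "will be assessed via phone/email/text using the Pillsy app weekly for the first 4 weeks and bi-weekly thereafter"; no end is stated, and GI symptoms are the only example given.
- **Record data in pregnancy.** At the 24-28 and 34-36 week visits the team abstracts illness, infection, new medication and changes in health status. Exploratory Aim 1 extracts gestational hypertension, pre-eclampsia and gestational diabetes. Section VI.e follows women through the EHR up to labor and delivery admission.
- **Delivery.** Section VI makes delivery a data-collection point. Section VI.e lists maternal blood, cord blood, placenta and, after discharge, abstraction of pertinent maternal and infant data ("i.e., route of delivery, infant weight, and infant length").
- **Analysis.** Section XIII compares counts of serious and other adverse events between groups.

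The documents contain no definition of a serious event, no collection window, no newborn safety item and no postpartum safety contact.

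**The concern.** A rule that requires zero documented events gets easier to pass as fewer events reach the record. Here the source named in the safety plan is the participant's own report, the structured tool at pick-up visits covers GI symptoms, and the scheduled pick-ups end at about 38-39 weeks although exposure continues to delivery. The items named for the post-discharge abstraction do not include gestational age at birth, fetal loss, neonatal intensive care admission, congenital anomaly or serious maternal events of the birth admission.

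Aim 4 rests partly on this rule. If birth and newborn events are captured by chance, a finding of tolerability could reflect how events were sought, and the infant could be left out of the safety comparison for a product taken during pregnancy.

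**Working it through.** The plan states no expected serious-event rate and no calculation behind the 40 women, so there is no figure to reproduce. The check asks how strongly the zero-event part of the rule depends on capture.

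**Inputs**
- n = 40 women (Section 2.I). Also n = 34, which is 40 × 0.85, if withdrawals reach the 15% feasibility limit in Section VI.c.
- p = true share of women (mother-infant pairs) with a serious event. Assumed at 1% and 5%; the documents give no rate.
- s = share of those events that reach the safety record. Assumed at 1, 0.5 and 0.1.

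**Formula**

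P(zero documented serious events) = (1 − p × s)^n, treating women as independent.

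**Worked cases, n = 40**
- p = 5%, s = 1: 0.95^40 = 0.13
- p = 5%, s = 0.5: 0.975^40 = 0.36
- p = 5%, s = 0.1: 0.995^40 = 0.82

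| n | p | Expected events (n × p) | Full capture | Half | One in ten |
|---|---|---|---|---|---|
| 40 | 1% | 0.4 | 67% | 82% | 96% |
| 40 | 5% | 2.0 | 13% | 36% | 82% |
| 34 | 1% | 0.34 | 71% | 84% | 97% |
| 34 | 5% | 1.7 | 17% | 42% | 84% |

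At s = 0 the probability is 100% for any p. At 5% the outcome depends heavily on capture. At 1% zero events is the likeliest result even with perfect capture, and capture matters less.

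**What a zero count could show at best.** With full capture and no events in 40 women, the one-sided 95% upper limit is 1 − 0.05^(1/40) = 7.2%. With 34 women it is 1 − 0.05^(1/34) = 8.4%. With incomplete capture these limits apply only to recorded events.

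**What full capture does to a literal zero rule.** At p = 5%, full capture passes the rule 13% of the time, and so fails it 87% of the time, even if no event is due to the product. Better data collection alone would therefore replace one problem with another.

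**The case against.** The strongest reply is that the plan has more routes to a serious event than participant report. Staff must report whatever they discover. They open the record at two visits and follow women to admission. They collect cord blood and placenta at birth, and under the COVID-19 changes midwives help obtain the delivery samples and the PI is alerted. They return to the record after discharge. Tolerability contacts have no stated end, and Section VII pays for labor and delivery as a data-collection visit. The after-discharge data are described as pertinent, and this protocol sometimes uses *i.e.* to introduce examples, so the three named items may not be exhaustive. Finally, a zero serious-event count does not by itself make the product tolerable.

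All of this stands, and it limits the point. A reader might infer that the tolerability rule can be met simply by not looking, or that birth events reach the record only if volunteered. The documents do not support either reading. What remains is that none of these routes asks for serious birth or newborn events, no definition tells staff which events count, and nothing carries record data into the event count or the rule.

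A reader might also turn to the background rates in Section 1 ("preterm birth rates range between 18.5% and 34.8"% in some neighborhoods, against 9.6% nationally and 10.3% in Illinois), multiply by 40 (7.4 to 13.9, 3.8 and 4.1 preterm births), and call these missed serious events. That does not follow. The documents do not say that preterm birth counts as serious. Eligibility sets no neighborhood criterion, and it excludes multiple pregnancy, premature rupture of membranes, tobacco, alcohol and drug use, and type 1 or 2 diabetes, so the neighborhood rates need not apply.

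**Conclusion.** The point holds as a gap in systematic collection and in linkage. Serious events of the birth admission and the newborn have no planned item, and EHR data are not tied to the between-group comparison in Section XIII or to the rule in Section VI.c. Incomplete capture makes the serious-event half of that rule easier to meet, and a reported zero could not be taken as absence of events.

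The size is a sensitivity range, not an estimate. Going from full to one-in-ten capture raises the chance of a zero count from 13% to 82% at a 5% true rate, and from 67% to 96% at 1%. Both the rate and the capture share are assumptions. The documents do not show that capture is low; they leave it unspecified. The change is worth making because it is cheap and improves the evidence for Aim 4.

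**What to change.** 1. **Section XIV.** Name the sources as events reported by participants, discovered by staff, or found in the maternal and infant record through discharge after delivery. State which events count as serious and the period over which they are collected.
2. **Section VI.e, post-discharge abstraction.** Add gestational age at birth, live birth or fetal loss, neonatal intensive care admission, congenital anomaly, and serious maternal events of the birth admission.
3. **Section XIII.** Classify these events before unblinding and include them, by arm, in the comparison of serious events with exact confidence intervals.
4. **Section VI.c.** Restate the serious-event part of the tolerability criterion as a comparison between arms. Without this step, background obstetric events could fail a literal zero rule whatever the product does.

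Cost: a few more fields in an abstraction that is already planned. More serious events will be counted in both arms, and the criterion will no longer be a simple zero count. With about 20 women per arm (assuming equal allocation, which the plan does not state), the comparison will be imprecise: even zero events in an arm leaves a one-sided 95% upper limit of 1 − 0.05^(1/20) = 13.9%. It should be reported as descriptive.
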